**1.0 Purpose of the study:**

**Aim 1 will characterize PD-MCI (Parkinson's disease mild cognitive impairment), PDN (Parkinson's disease without cognitive impairment), and HA (healthy adult) spoken discourse, cognitive, and motor speech profiles.** Phase 2 biomarker development requires robustly characterized cohorts in which to test candidate biomarkers. Using a standardized battery of cognitive, language, and motor speech tests PD participants will be assigned to PD-MCI (single/multi-domain) or PDN groups. We propose collecting spoken discourse samples using standardized elicitation protocols. The same tasks will be extracted from the extant HA database. Researchers will transcribe, code, and analyze discourse samples. Group differences (including sub-analyses for single and multi-domain MCI subtypes), elicitation stimuli effects, and group x stimuli interactions will be examined using multivariate and mixed-design ANOVA procedures.

**Aim 2 will develop and evaluate the classification accuracy of an optimally weighted discourse classification function for PD-MCI and PDN.** We propose using discriminant function analysis to identify an optimized composite variable that best predicts PD-MCI, PDN, and HA group membership. Sensitivity/specificity analyses, positive/negative predictive values, and receiver operating characteristic curves will be used to evaluate the discourse classification function properties.

The **primary endpoint** is an optimally weighted discourse function that can classify PD-MCI with > 80% sensitivity/specificity.

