**2.0 Background / Literature Review / Rationale for the study:**

Individuals with Parkinson's disease (PD) have a 6-fold increased risk of dementia. PD mild cognitive impairment (PD-MCI) is thought to be a transitional state to dementia for

many of those affected. **Difficulties monitoring early cognitive impairments, and concomitant delays in treatment initiation, are major barriers** to the accurate diagnosis of and the development of interventions for cognitive impairments in PD. A biomarker is any characteristic that can be objectively measured and indicates normal/pathogenic processes or responses to therapeutic interventions. Biomarkers can be genetic markers, neural markers, and observable behaviors. In the absence of neuropsychological findings, early dementia can still be detected in spoken discourse. Thus, a **spoken discourse biomarker** can be a valuable supplement to extant neuropsychological evaluation for **monitoring cognitive-linguistic changes in real world environments**. The **long-term objective** of this research is to improve the early and accurate diagnosis of PD cognitive impairment with a reliable spoken discourse biomarker. Research shows that discourse features including grammar errors, information content/efficiency, coherence, and verbal disfluencies hold promise for detecting PD cognitive impairments. Additionally, our pilot suggests that an optimally weighted composite variable, and no one single variable, is best able to discriminate PD spoken discourse. A **major barrier** is the absence of a spoken discourse biomarker that has been rigorously developed and tested on a meticulously-characterized cohort of PD-MCI, PD without cognitive impairment (PDN), and healthy adults (HA). Using the Fit-for-Purpose framework, **the goal of the proposed research is to complete a Phase 2 spoken discourse biomarker study**. The **overarching hypothesis** is that PD-MCI and PDN will have unique profiles of spoken discourse impairments that are distinguishable from each other and from HA.

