## **4.0 Sample Size:**

We will enroll 86 PD participants (43 individuals with PD and normal cognition and 43 individuals with PD mild cognitive impairment). Data from 43 age/education/sex matched HA will be sampled from an extant repository.

Sample sizes for ANOVA and DFA were calculated using G\*Power. For Aim 1, a sample of 129 participants for MANOVA procedures with 3 IVs (PD-MCI, PDN, HA), 15 dependent variables (6 canonical variables), and up to 3 covariates will detect a minimum of  $f^2$  of 0.16 (medium-sized effects) with power of 0.90, and  $\alpha=0.05$ . The available effect size estimates for the 8 candidate discourse variables range from  $f^2$  of 0.33 to 0.50 (medium to large effects). With the smallest anticipated effect size based on our pilot data ( $f^2 = .33$ ) 129 participants in a mixed ANOVA with 2 IVs (Group [3 levels]) and Task [2 levels]) with up to 2 covariates will yield power of 0.86,  $\alpha=0.05$ . At the highest estimated effect size ( $f^2 = .50$ ), the same sample size will yield power of 0.99,  $\alpha=0.05$ . For **Aim 2**, DFA procedures with 3 groups and 8 discourse variables with 129

participants will detect  $f^2$  of .10 (small-medium effects) with power of 0.90,  $\alpha=0.05$  and power of 0.85, if  $\alpha=0.025$ . For the sensitivity and specificity analyses a sample of 129 participants will detect sensitivity and specificity values of 0.83 or higher with a 90% confidence interval precision of 0.10, given an expected disease (PD-MCI) prevalence of 30%, a conservative prevalence estimate. This precision level is consistent with guidelines for Phase 2 studies.

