**Aim 2**

The spoken discourse measure data will be used in a canonical discriminant function analysis (DFA) to identify the optimal discourse classification functions that separate groups. DFA is a multivariate procedure that is used to predict group membership. In our

case, where there are > 2 diagnostic groups, Wilks' lambda values, in a stepwise approach, will be used to identify the final set of variables that account for the maximal variance for group differences. This step will eliminate variables that do not contribute significantly to group variance. Redundant variables will also be deleted. The DFA approach will yield multiple potential models that will be evaluated for classification accuracy using sensitivity and specificity analyses. Receiver operating characteristic curves will be used to evaluate discriminant function accuracies as discrimination thresholds vary.

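### The primary endpoint does not say in whom specificity is measured: the Aim 2 wording points to PDN, the sample-size calculation to PDN pooled with healthy adults, and the two can give opposite verdicts

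*Combined protocol and SAP*

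**What the plan says.** Section 1.0 states that the primary endpoint "is an optimally weighted discourse function that can classify PD-MCI with > 80% sensitivity/specificity". The case group is PD-MCI; no non-case group is given.

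Other parts of the plan bear on who the non-cases are:

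- **Towards PDN only.** The lead sentence of Aim 2 in Section 1.0 describes an "optimally weighted discourse classification function for PD-MCI and PDN". The long-term objective in Section 2.0 is to "improve the early and accurate diagnosis of PD cognitive impairment with a reliable spoken discourse biomarker", a question about people who already have Parkinson's disease.
- **Towards PDN pooled with HA.** The next sentence of Aim 2 proposes to "identify an optimized composite variable that best predicts PD-MCI, PDN, and HA group membership". Section 4.0 states: "For the sensitivity and specificity analyses a sample of 129 participants will detect sensitivity and specificity values of 0.83 or higher", and adds "given an expected disease (PD-MCI) prevalence of 30%, a conservative prevalence estimate". The same section says: "Data from 43 age/education/sex matched HA will be sampled from an extant repository". The total of 129 is those 43 plus the 86 enrolled PD participants.

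Section 8.0 (Proposed Data Analysis, Aim 2) describes a discriminant function analysis (DFA) for a setting "where there are > 2 diagnostic groups". It says that candidate models will be judged by sensitivity, specificity and ROC curves. It does not say how three groups become two for that purpose, or which score is to be thresholded for the ROC curve.

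**The concern.** Specificity has no value until its denominator is named. Here two denominators are available, 43 PDN or 86 PDN plus HA, and different parts of the plan support each.

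The two do not answer the same question. PDN share the disease with PD-MCI and differ in cognition. HA do not have Parkinson's disease, so leaving them out of the PD-MCI class does not show that the function separates impaired from unimpaired cognition within Parkinson's disease. If HA are easier to classify than PDN, they can lift a pooled specificity above 80% while specificity among people with Parkinson's disease stays below it. Nothing in the plan ties the endpoint to the PDN result, so the comparator could be settled after the classification table has been seen. Predictive values, which Section 1.0 also plans, depend on the same choice.

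**Working it through.** **Inputs.** Criterion: strictly above 80% (Section 1.0). Groups: 43 PD-MCI, 43 PDN, 43 HA (Section 4.0). Precision: expected value 0.83, 90% confidence interval, precision 0.10 read as a half-width, prevalence 30% (Section 4.0). All 43 per group are assumed evaluable. Correct, for a non-case, means not labelled PD-MCI.

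**1. The plan's own figure.** For sensitivity, N = z² p(1 − p) / (d² × prevalence).

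- Cases needed: 1.645² × 0.83 × 0.17 / 0.10² = 38.2, so 39.
- Total at 30% prevalence: 38.2 / 0.30 = 127.3, so 128. The plan states 129, so the figure is reproduced to within one participant.
- Literal split of 129 at 30%: 38.7 cases and 90.3 non-cases. Only 43 PDN exist, so HA must be among the non-cases.
- The same formula for PD participants only, at 43/86 = 50%: 38.2 / 0.50 = 76.4, so 77, which is within the 86 enrolled.

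**2. What each denominator requires.**

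- PDN only: 34/43 = 79.1% fails and 35/43 = 81.4% passes, so at most 8 PDN may be called PD-MCI.
- Pooled: 68/86 = 79.1% fails and 69/86 = 80.2% passes, so at most 17 errors in total, however they are divided.

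A pooled pass is therefore compatible with anything from 0 to 17 PDN errors. Counts of 0 to 8 also pass the PDN-only rule; counts of 9 to 17 fail it. At the pooled boundary, PDN correct = 69 − HA correct:

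| HA correct | PDN correct | PDN errors | PDN specificity |
|---|---|---|---|
| 35/43 | 34/43 | 9 | 79.1% |
| 39/43 | 30/43 | 13 | 69.8% |
| 41/43 | 28/43 | 15 | 65.1% |
| 43/43 | 26/43 | 17 | 60.5% |

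A pooled pass with a PDN-only failure needs at least 35 HA correct and at most 34 PDN correct, so HA must do better than PDN. The opposite flip is arithmetically possible: PDN 35/43 passes alone, but with HA at 33/43 the pooled figure is 68/86 and fails.

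**3. Illustration under assumed true values, none of which is in the documents.** With independent binomial errors, PDN specificity 0.70 and HA specificity 0.95, the observed pooled figure exceeds 80% with probability about 0.77 and the PDN-only figure with probability about 0.07. Over PDN 0.65 to 0.75 and HA 0.90 to 0.98, the ranges are 0.31 to 0.97 (pooled) and 0.015 to 0.22 (PDN only).

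**4. Precision with PDN only.** Half-width = 1.645 × √(p(1 − p)/n).

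- p = 0.83: 0.094 with n = 43; 0.067 with n = 86.
- p = 0.80: 0.1003 with n = 43; 0.071 with n = 86.

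**5. Predictive values.** With sensitivity and specificity both 0.83, the positive predictive value is 0.83/(0.83 + 0.17) = 0.83 at 43 cases to 43 non-cases, and 0.83/(0.83 + 2 × 0.17) = 0.71 at 43 to 86.

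**The case against.** The strongest reply is that the plan has in effect chosen pooling. Section 4.0 is the only place that sizes these analyses. Its arithmetic fits 129 closely, and its 30% lies just below 43/129 = 33%, in keeping with being called conservative. HA are also a legitimate comparator, since the hypothesis in Section 2.0 expects the PD groups to differ from HA as well as from each other. The study is an observational Phase 2 biomarker study with no action attached to passing 80%, and a three-group classification table would probably show the PDN errors anyway.

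Much of this stands. The sizing is not neutral; it leans towards pooling. But it is an inference from a sample-size sentence, not a definition of the endpoint. The total of 129 serves every calculation in Section 4.0, and the plan does not say in which population the 30% holds. The sizing also conflicts with the Aim 2 lead sentence. HA can remain in the function and be reported without being in the endpoint's denominator. A table that shows the PDN errors does not say which figure decides the endpoint.

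A reader might also infer that a PD participant labelled HA has no defined place in the count. Ordinary definitions settle that: such a PDN participant was not called PD-MCI, and such a PD-MCI participant was missed. Nor do the documents support the inference that the study is too small for a PDN-only comparison, since at 0.83 it needs 39 per group and has 43.

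**Conclusion.** The point holds. The primary endpoint's specificity has no stated denominator, and the plan's own passages support two that can reach opposite verdicts on the same data. If the 129-participant sizing is followed, the >80% target can be met with PDN specificity as low as 60.5%, which would not answer the stated question about cognitive impairment in Parkinson's disease.

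Two stronger readings should be avoided. One is that a pooled pass means at least 9 PDN errors: the discordant counts are only part of what a pooled pass allows, and the extreme of 17 needs every HA to be correct. The other is that the endpoint will be met spuriously. The documents give no expected specificity for either group, so the chance of a discordant verdict is unknown. If the two groups are classified about equally well, pooling changes little beyond precision.

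The counts rest on 43 fully evaluable participants per group. The comparator should be fixed before results are seen.

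**What to change.** In Sections 1.0 and 8.0 (Aim 2), define the primary-endpoint sensitivity, specificity, predictive values and ROC curve as PD-MCI (n = 43) versus PDN (n = 43).

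- Keep the three-group DFA. Use the PD-MCI classification from the final selected model, since Section 8.0 expects several candidates, and count any other label as not PD-MCI.
- Name in advance one score for the ROC curve, such as the posterior probability of PD-MCI.
- Report specificity in HA separately, as secondary.
- State that predictive values at the enrolled 50% ratio are not population values.
- In Section 4.0, restate the precision on 43 cases and 43 non-cases: 90% half-width 0.094 at 0.83 and 0.1003 at 0.80.

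This needs no new participants, data or models. The ROC score is a new specification, because the plan names none. The costs are a wider interval for specificity than pooling would give, a half-width marginally over 0.10 if the true value is at the 0.80 threshold, and probably a lower specificity estimate.

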**2.0 Background / Literature Review / Rationale for the study:**

Individuals with Parkinson's disease (PD) have a 6-fold increased risk of dementia. PD mild cognitive impairment (PD-MCI) is thought to be a transitional state to dementia for

many of those affected. **Difficulties monitoring early cognitive impairments, and concomitant delays in treatment initiation, are major barriers** to the accurate diagnosis of and the development of interventions for cognitive impairments in PD. A biomarker is any characteristic that can be objectively measured and indicates normal/pathogenic processes or responses to therapeutic interventions. Biomarkers can be genetic markers, neural markers, and observable behaviors. In the absence of neuropsychological findings, early dementia can still be detected in spoken discourse. Thus, a **spoken discourse biomarker** can be a valuable supplement to extant neuropsychological evaluation for **monitoring cognitive-linguistic changes in real world environments**. The **long-term objective** of this research is to improve the early and accurate diagnosis of PD cognitive impairment with a reliable spoken discourse biomarker. Research shows that discourse features including grammar errors, information content/efficiency, coherence, and verbal disfluencies hold promise for detecting PD cognitive impairments. Additionally, our pilot suggests that an optimally weighted composite variable, and no one single variable, is best able to discriminate PD spoken discourse. A **major barrier** is the absence of a spoken discourse biomarker that has been rigorously developed and tested on a meticulously-characterized cohort of PD-MCI, PD without cognitive impairment (PDN), and healthy adults (HA). Using the Fit-for-Purpose framework, **the goal of the proposed research is to complete a Phase 2 spoken discourse biomarker study**. The **overarching hypothesis** is that PD-MCI and PDN will have unique profiles of spoken discourse impairments that are distinguishable from each other and from HA.

### 3.0 Inclusion and Exclusion Criteria:

Only individuals with PD will be newly recruited and enrolled as part of the study. Healthy adult data will be extracted from extant databases (publicly available) from NIH-funded studies.

Inclusion Criteria Person with Parkinson's disease without cognitive impairment

- Age 50-90 years
- Diagnosis of idiopathic Parkinson's disease (UK Brain Bank criteria) made by a movement disorders specialist
- Under the care of a movement disorders specialist for a minimum of 1-year duration
- Native monolingual English speaker
- Hoehn & Yahr score between 1.5 and 4
- Grade 10 education, or higher
- Sufficient vision and hearing (aided or unaided) for all experiment tasks
- Montreal Cognitive Assessment (or MoCA-converted MMSE score) greater than or equal to 25
- No subjective complaints of cognitive difficulty or word finding issues

Inclusion Criteria Person with Parkinson's disease mild cognitive impairment

- Age 50-90 years
- Diagnosis of idiopathic Parkinson's disease (UK Brain Bank criteria) made by a movement disorders specialist

- Under the care of a movement disorders specialist for a minimum of 1-year duration
- Native monolingual English speaker
- Hoehn & Yahr score between 1.5 and 4
- Grade 10 education, or higher
- Sufficient vision and hearing (aided or unaided) for all experiment tasks
- Montreal Cognitive Assessment (or MoCA-converted MMSE score) greater than or equal to 17
- Subjective complaints of cognitive difficulty or word finding issues, without significant impact on activities of daily living

**Inclusion Healthy Adults (from extant data base – no new recruiting)**

- Age 50-90 years
- Montreal Cognitive Assessment (or MoCA-converted MMSE score) greater than or equal to 26
- Native monolingual English speaker
- Grade 10 education, or higher
- Sufficient vision and hearing (aided or unaided) for all experiment tasks

**Exclusion Criteria Neurological injury or disease (other than PD for the PD cohort)**

- History of unmanaged or untreated depression or major psychiatric illness
- History of deep brain stimulation surgery (DBS)
- Diagnosis of Dementia with Lewy Bodies

**Hearing and Vision Screening.** PD participants will complete the protocol using their typical vision and hearing devices. PD participants with pure tone averages > 41 dB (either ear), who do not have their own assisted listening device, will be fitted with a personal amplifier only during test/task instructions and test item presentation. Participants will complete vision acuity and field screening tasks to confirm sufficient visual acuity (aided or unaided) and in-tact visual fields for the discourse tasks.

## **4.0 Sample Size:**

We will enroll 86 PD participants (43 individuals with PD and normal cognition and 43 individuals with PD mild cognitive impairment). Data from 43 age/education/sex matched HA will be sampled from an extant repository.

Sample sizes for ANOVA and DFA were calculated using G\*Power. For Aim 1, a sample of 129 participants for MANOVA procedures with 3 IVs (PD-MCI, PDN, HA), 15 dependent variables (6 canonical variables), and up to 3 covariates will detect a minimum of  $f^2$  of 0.16 (medium-sized effects) with power of 0.90, and  $\alpha=0.05$ . The available effect size estimates for the 8 candidate discourse variables range from  $f^2$  of 0.33 to 0.50 (medium to large effects). With the smallest anticipated effect size based on our pilot data ( $f^2 = .33$ ) 129 participants in a mixed ANOVA with 2 IVs (Group [3 levels]) and Task [2 levels]) with up to 2 covariates will yield power of 0.86,  $\alpha=0.05$ . At the highest estimated effect size ( $f^2 = .50$ ), the same sample size will yield power of 0.99,  $\alpha=0.05$ . For **Aim 2**, DFA procedures with 3 groups and 8 discourse variables with 129

participants will detect  $f^2$  of .10 (small-medium effects) with power of 0.90,  $\alpha=0.05$  and power of 0.85, if  $\alpha=0.025$ . For the sensitivity and specificity analyses a sample of 129 participants will detect sensitivity and specificity values of 0.83 or higher with a 90% confidence interval precision of 0.10, given an expected disease (PD-MCI) prevalence of 30%, a conservative prevalence estimate. This precision level is consistent with guidelines for Phase 2 studies.

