Sentence Intelligibility Test (SIT-5). Set of 11-sentences generated for each participant. Sentences are phonetically balanced and are read aloud by the participant. Measure of speech intelligibility
Standardized oral reading passage (speech rate and intelligibility)
Brief motor speech exam
Demographic form (attached)
National Adult Reading Test
Neuropsychological Measures Used in Primary Analyses and to Classify Participants into MCI-PD from PDN (no cognitive impairment) groups
Trail Making Test-A (In-person testing)
Trail Making Test-B (In person testing)
10-points Clock Drawing Test + Clock copying
Free and Cued Selective Reminding Test from the Arizona Battery of Communication Disorders of Dementia (In-person testing)
Brief Visuospatial Memory Test-Revised
Semantic Fluency-animals
Digit span forward and backward
Stroop Color-word Interference
Boston Naming Test (30-item version)
Verb Naming Subtest – Northwestern Assessment of Verbs and Sentences
Sentence Production Priming subtest of the Northwestern Assessment of Verbs and Sentences
Pyramids and Palm Trees Test - object semantics
CERAD 10-Word List (Remote testing)

Discourse Sampling (main study outcome measure)

Using standardized spoken discourse elicitation stimuli and instructions, participants will be asked to generate a story about a series of events occurring in: 1) a series of six black and white line drawings and 2) a wordless picture book. Participants will generate a maximum of four spoken discourse samples. Each discourse sample is estimated at 2 to 4 minutes in length. Audio files will be transcribed using a HIPAA compliant transcription service/software. Once transcribed, files will be coded in [name] lab for a number of discourse (e.g., story structure, information content), speech (e.g., pauses, number of words), and language variables (e.g., grammar/syntax).

Proposed Data Analysis

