**Aim 1**

Multivariate ANOVA statistical procedures will be used to examine group differences on neuropsychological test measures and spoken discourse measures. Follow-up univariate ANOVAs and Tukey's post-hoc tests will be used to further examine significant individual variables from the multivariate testing and to examine group contrasts (healthy controls, PD without cognitive impairment, and PD-MCI). If required based on group differences in descriptive variables age, sex, depression measure scores, and education will be entered as covariates.

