## **15.0 Risks to Participants:**

The risks involved with this study are not substantially different from those associated with typical clinic visits. Participants may experience fatigue owing to the duration of the protocol. If enrolled in the remote protocol, participants may experience fatigue commonly associated with using videoconferencing software for extended periods of time. In our experience administering a similar duration neuropsychological assessment protocol within the Ontario Neurodegeneration Diseases Initiative, fewer than 5% of 160 PD participants required two data collection visits.

Some participants may experience a sense of emotional discomfort from being video/audio recorded during these sessions. Video and audio recording are routine during Parkinson's-disease related clinical sessions.

We anticipate that all participants with cognitive impairments will be aware that they have cognitive issues. However, it is possible that our testing may reveal deficits of which the participant was previously unaware and thus may present a potential risk of distress associated with this concern.

Some participants may perceive a sense of nervousness when completing mood and cognitive testing, particularly the depression measure. Participants will be able to refuse any task that makes them uncomfortable.

There are no anticipated physical risks associated with this study.

While efforts will be taken to protect participant confidentiality, there is always a risk that confidentiality may be breached. The primary risk of breaching confidentiality in the current study arises from the need to audio/video record data collection sessions.

There are no anticipated social or legal risks.

There are no costs associated with the study. Participants' parking will be covered for all visits. We will also provide a nominal study participation fee to help accommodate for travel and time-related expenses.

*Risk level.* The overall risk level is low and impact to participants is anticipated to be minimal. This assessment is based on a number of projects in the PI's lab that employ similar procedures, research designs, and methods.

*Minimizing Risks.*

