*Withdrawing from the Study.* Consent is voluntary. A participant is free to withdraw from the study at any point in time. If a participant withdraws from the study, a summary of their treatment progress (up to the point of withdrawal) will remain in the research record and may be included in the analysis. However, no further data will be collected. The data collected from the participants up and until the point of withdrawal will remain in the study.

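### The Group x Task discourse analysis is a mixed ANOVA that cannot use a participant with only one task; a suitably specified linear mixed model can, and matches it when data are complete

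*Combined protocol and SAP*

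**What the plan says.** Section 1.0 (Aim 1) says that group, stimulus and "group x stimuli interactions will be examined using multivariate and mixed-design ANOVA procedures". Section 4.0 powers this as "129 participants in a mixed ANOVA with 2 IVs": Group with three levels and Task with two. The Aim 1 analysis text in section 8.0 covers only the MANOVA ("Multivariate ANOVA statistical procedures will be used to examine group differences on neuropsychological test measures and spoken discourse measures"), with follow-up ANOVAs and Tukey tests. It gives no Group x Task model and no rule for missing data.

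On data completeness:
- Section 8.0, Discourse Sampling, uses two types of stimulus and sets an upper limit only: "Participants will generate a maximum of four spoken discourse samples".
- Section 15.0: "Participants will be able to refuse any task that makes them uncomfortable". Section 16.0 repeats the right to decline any task, in general terms.
- Section 17.0 lets staff end testing for distress, or for fatigue that rest does not relieve.
- Section 15.0, on withdrawal: "The data collected from the participants up and until the point of withdrawal will remain in the study".
- Section 4.0: "We will enroll 86 PD participants (43 individuals with PD and normal cognition and 43 individuals with PD mild cognitive impairment"), with no allowance for missing tasks. The 43 healthy adults (HA) come from an existing repository.

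**The concern.** A two-level within-person factor in a standard mixed ANOVA needs a value for each task from every person. Someone who completes one task and declines the other is removed, and the task they did complete is lost with them. The plan therefore keeps partial discourse data that its named method cannot use.

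If those who stop early tend to be the weaker performers, and more often have PD-MCI, dropping them makes the PD-MCI group look better than it is. The contrasts of PD-MCI with PDN and with HA then shrink. HA cases can be selected with both tasks present, so the loss may fall only on the PD groups.

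**Working it through.** **1. The plan's own figure.** Section 4.0 states power 0.86 at the smallest effect, written as f² = .33, with N = 129 and α = 0.05. For the group effect, λ = f²·N·m/(1+(m−1)ρ), with m = 2 tasks; ρ is not given.
- f² = .33, ρ = 0.5: λ = 0.33 × 129 × 2/1.5 = 56.8, power about 1.00.
- .33 read as f: f² = 0.1089. Power is 0.998 at ρ = 0 and 0.935 at ρ = 0.9. With one measure per person, λ = 0.1089 × 129 = 14.0 and power is 0.923.
- The nearest simple setting, a fixed-effects ANCOVA with 4 numerator df, gives 0.853 but is not the design described.

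The 0.86 does not reproduce. That is a separate matter, and nothing here endorses the figure.

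**2. Power lost by dropping people (f = .33).** Assume 5%, 10% or 20% of the 86 PD participants miss a task: 129 − 4 = 125, 129 − 9 = 120, 129 − 17 = 112 complete.

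| Complete N | 129 | 125 | 120 | 112 |
|---|---|---|---|---|
| 2 numerator df | 0.923 | 0.914 | 0.902 | 0.879 |
| 4 numerator df | 0.853 | 0.839 | 0.821 | 0.789 |

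**3. Complete data, one value per task.** In three simulated data sets of 3 x 43, the F values for mixed ANOVA and REML random-intercept model were: group 7.6602 and 7.6600, 12.7915 and 12.7917, 3.2143 and 3.2144; interaction 1.0498, 1.2128 and 0.1545 under both. The match requires a non-negative between-person variance estimate.

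**4. Task 2 missing, PD-MCI versus PDN.** Assumptions: true gap 0.5 SD on both tasks, between-task correlation 0.6, task 2 missing mainly in people with low task 1 scores (missing at random, MAR), 4,000 simulated studies per setting.

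| Missing, PD-MCI / PDN | Understatement, complete cases (SD) | Share of 0.5 SD | Likelihood bias (SD) |
|---|---|---|---|
| 5% / 2% | 0.037 | 7% | −0.001 |
| 10% / 5% | 0.054 | 11% | 0.001 |
| 15% / 5% | 0.097 | 19% | 0.006 |

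A separate simulation at these rates gave about 0.02 to 0.07 SD, so the range to carry forward is roughly 0.02 to 0.10 SD. If missingness is unrelated to performance (MCAR) there is no bias, and complete-case variance is 2% to 11% larger.

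**5. Dependence on the mechanism.** PD-MCI minus HA, true value −0.600, true interaction 0, ρ = 0.5, assumed missing 20% in PD-MCI, 6.7% in PDN and none in HA (about 11.5 people dropped):

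| Mechanism | Group: ANOVA | Group: mixed model | Interaction: ANOVA | Interaction: mixed model |
|---|---|---|---|---|
| MAR | −0.488 | −0.602 | −0.070 | 0.007 |
| Depends on unseen task 2 (MNAR) | −0.487 | −0.545 | +0.076 | +0.116 |

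Under MCAR the SD of the group estimate is 0.202 (ANOVA) against 0.191 (mixed model), and of the interaction 0.236 against 0.231. A person with one task says almost nothing about the difference between tasks.

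**6. Several samples per task.** Up to four samples over two stimulus types could mean two per task. Take complete data (3 x 43), participant variance 0.5 of a total of 1, no true interaction, 4,000 runs. Interaction type I error at nominal 5%:

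| Participant-by-task variance | ANOVA on task means | Mixed model, participant intercept only, all samples |
|---|---|---|
| 0 | 5.4% | 5.2% |
| 0.05 | 4.7% | 7.1% |
| 0.10 | 4.4% | 8.9% |
| 0.20 | 4.9% | 16.2% |

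Arithmetic check at 0.20, taking residual variance as 1 − 0.5 − 0.20 = 0.30. The interaction mean square has expectation 0.30 + 2 × 0.20 = 0.70. The intercept-only model pools 126 participant-by-task df with 129 × 2 = 258 replicate df, giving 0.30 + 0.40 × 126/384 = 0.431. The F statistic is inflated by 0.70/0.431 = 1.62. The 5% critical value of F(2, 384) is 3.02, so the true rate is P(F > 3.02/1.62), about 16%.

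**The case against.** The strongest objection is that the amount of missing data may be small. No rate is given. Each sample is expected to last 2 to 4 minutes, most participants should finish in one visit, and breaks and a second visit are offered. Section 15.0 reports that fewer than 5% of 160 PD participants needed two visits in a protocol of similar length; that speaks to tolerability and is not a missing-task rate. The section 15.0 refusal sentence follows a remark about mood and cognitive testing, although section 16.0 is general. If there are two samples per task, losing one still leaves a task mean and nobody is dropped. All of this stands. It limits the size of the benefit, but the choice of model remains sound because the two methods agree when nothing is missing.

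Stronger readings that the documents do not support:
- *A mixed model avoids the bias.* Only under MAR or MCAR. Refusal through discomfort may depend on the unseen performance; in the MNAR simulation the mixed model was still biased for group and worse than ANOVA for the interaction.
- *Any mixed model on all samples is free of downside.* With repeated samples per task, a participant intercept alone does not equal the mixed ANOVA (step 6).
- *The plan prescribes deletion of incomplete cases, or expects uneven data.* It says neither. Deletion follows from the standard method, and an upper limit of four samples does not establish imbalance.
- *The primary endpoint is compromised.* The Aim 2 discriminant function does not use this model.

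**Conclusion.** The point holds as a low-cost improvement to one Aim 1 analysis. The plan names a method that in standard form discards participants with one task, while allowing that situation to arise and retaining the data. With complete, balanced data and non-negative variance estimates, the mixed model gives the same F tests.

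With a task missing at random, it removes a complete-case bias of roughly 0.02 to 0.10 SD in a 0.5 SD group contrast, at assumed rates of 5% to 15% in PD-MCI. Those rates, the correlations and the variance components are assumptions. The precision gain is modest for the group effect and close to nil for the interaction. Bias under MNAR remains. The MANOVA and the Aim 2 discriminant analysis, which normally also use complete cases, are left as they are and still lack a missing-data rule.

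**What to change.** In sections 1.0 and 4.0 replace the mixed-design ANOVA for the discourse measures, and carry the change into the Aim 1 analysis text in section 8.0. Suggested content: a linear mixed model (REML) with group, task, group x task and the Aim 1 covariates as fixed effects, including every participant with at least one task. State one of two forms:
- one mean per participant per task, with a participant random intercept; or
- all individual samples, with participant and participant-by-task random effects.

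Also state how many samples are planned per task. Add a short MNAR sensitivity analysis, for example shifting the unobserved task values downward over a stated range and reporting the group and interaction contrasts at each shift. Say that the model reproduces the mixed ANOVA when data are complete and balanced, without treating this as support for the 0.86 power figure.

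The cost is wording, slightly more analysis work and reliance on MAR in the main analysis. No new data are needed. The change should be made before results are seen.
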